1.0 PURPOSE

This study will address a well-known neurological disorder for which there are limited effective treatments and an urgent need to find an efficacious management that could help prevent, or at least slow down the progress of this major public health problem.

- **Parkinson's disease (PD)** is a neurological disorder with evolving layers of complexity. It has long been characterized by the classical motor features of parkinsonism associated with Lewy bodies and loss of dopaminergic neurons in the Substantia Nigra. However, the symptomatology of Parkinson's disease is now recognized as heterogeneous, with clinically significant non-motor features. Similarly, its pathology involves extensive regions of the nervous system, various neurotransmitters, and protein aggregates other than just Lewy bodies. Parkinson's disease seems to result from a complicated interplay of genetic and environmental factors affecting numerous fundamental cellular processes. The complexity of Parkinson's disease is accompanied by clinical challenges, including an inability to make a definitive diagnosis at the earliest stages of the disease and difficulties in the management of symptoms at later stages.

2.0 SCOPE

Sample Size: 20 patients

10 patients will be designated to receive yFFP

10 patients will be designate to receive the placebo - .9% Saline with Riboflavin (Vitamin B2) additive

3.0 DEFINITIONS

FFP: fresh frozen plasma, not necessarily from a young donor

SAE: serious adverse event

SOP: standard operating procedure

yFFP: fresh frozen plasma from a young (18 – 25 year old), sex-identified donor

**INTRAVENOUS young FRESH FROZEN PLASMA (yFFP®) INVESTIGATIONAL TREATMENT FOR
PARKINSON'S DISEASE
PROTOCOL FOR CONTROLLED STUDY**

5.0 TRIAL STATUS

Current Status: Closed

Closure Date: January 2019

6.0 MATERIALS/EQUIPMENT

- Blood group-specific yFFP
- IV Starter Kit
- IV Catheter
- Plasma Warmer
- .9% Saline Solution
- Fresenius Kabi Blood Bag 200ml
- Riboflavin (Vitamin B2)
- Labels for Placebo

7.0 STUDY DESIGN & METHOD

The study is a prospective double-blind placebo-controlled trial, designed to evaluate the safety and efficacy of intravenous young Fresh Frozen Plasma at 12.5 ml/kg in each of two doses, two days apart (25 ml/kg total).

Patients in the Placebo group will receive infusions of 0.9% Sodium Chloride with Vitamin B2 at a volume rate equal to that of yFFP 12.5 ml/kg in each of two doses, also two days apart.

Consecutive patients are alternately assigned to one of the two treatment study groups, labeled 'yFFP' or 'Saline' group. Because yFFP is in short supply,

**INTRAVENOUS young FRESH FROZEN PLASMA (yFFP®) INVESTIGATIONAL TREATMENT FOR
PARKINSON'S DISEASE
PROTOCOL FOR CONTROLLED STUDY**

the trial manager is free to change the strict alternate allocation sequence, according to the blood types of yFFP available.

Each participant's condition will be classified as mild to moderate. Patients above 2.5 on the Hoehn and Yahr scale will not be eligible for the trial.

The primary outcome is the change in sum of the UPDRS scales 1-3 in the yFFP group compared with the placebo group.

There will be one study site, a secondary care clinic specializing in neurology and infusions (Houston, Texas).

Study will include 20 patients with Parkinson's disease.

Blinding will be achieved by preparing both yFFP and placebo (0.1% Riboflavin in normal saline) solution into identical bags. The Riboflavin is added to achieve indistinguishable color when compared to the yFFP. Labels, barcoded numbers and expiration dates for both the active and saline placebo will be indistinguishable. All infusion bags will be masked.

For the time frame, study day 0 is defined as the day of treatment allocation. Baseline evaluation and laboratory testing will be done then. The first infusion will be scheduled at most two weeks later, and the second infusion will occur two days after the first.

Physician assessments, caregiver surveys and blood tests will be completed at 4-weeks, 12-weeks and 24 weeks, to explore the duration of yFFP - and unspecific treatment effects.

Definition of end of study

The end of the study will be the last participant's final contact at 24 weeks.

The study duration will be eight months from study set-up to analysis and closure. An interim report will be produced at the 12-week point.

Serious Adverse Events (SAE) will be monitored for 14-days after final dose of yFFP or until resolution.

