10.0 SCREENING, RECRUITMENT AND CONSENT

Patients will be identified through the clinical site.

Strategies will be implemented to maximize awareness of the trial in the patient population and increase referrals to the recruiting centers (informative materials will be included as part of the study documents).

Patients will be given the "Patient Information Sheet" to read at least 24-hours before the screening visit, where they will be given the "Informed consent."

At the screening visit, there will be an opportunity for the participants to ask questions of a member of staff trained in all trial procedures, as delegated by the PI. The Principal Presenter or a co-investigator at each site will ensure that the participants meet the inclusion and exclusion criteria at the point of screening.

Patients will be telephoned within 2 days, and maximally 4 days after baseline testing to confirm eligibility to participate.

Screen failures may be rescreened ONLY where there is a short-term reason for ineligibility, such as non-availability for study visits due to planned holidays or an ongoing acute illness.

**INTRAVENOUS young FRESH FROZEN PLASMA (yFFP®) INVESTIGATIONAL TREATMENT FOR
PARKINSON'S DISEASE
PROTOCOL FOR CONTROLLED STUDY**

A screening log will be kept at site to document details of patients invited to be screened for participation in the study. For patients who decline or are ineligible, this will document any reasons available for nonparticipation (where provided). The log will ensure potential participants are only approached once.

The original signed consent form will be retained in the investigator site file, with a copy in the participant's medical notes, and a copy provided to the participant. The participant will specifically consent to their GP being informed of their participation in the study.

The right to refuse to participate without giving reasons will be respected.

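### Patients are allocated by alternation that the Trial Manager may override, with no random sequence or concealment, so the primary comparison is open to selection bias and has no randomisation basis

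*Combined protocol and SAP*

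**What the plan says.** Section 7.0 sets the allocation rule: "Consecutive patients are alternately assigned to one of the two treatment study groups, labeled 'yFFP' or 'Saline' group". Because the product is scarce, it adds that "the trial manager is free to change the strict alternate allocation sequence, according to the blood types of yFFP available". Section 20.0 has the same Trial Manager allocate at 1:1 and says nothing about how the sequence is produced or hidden.

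On timing, Section 7.0 says "study day 0 is defined as the day of treatment allocation. Baseline evaluation and laboratory testing will be done then". Section 10.0 then says: "Patients will be telephoned within 2 days, and maximally 4 days after baseline testing to confirm eligibility to participate".

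The plan has some safeguards. Under Section 10.0 an investigator "will ensure that the participants meet the inclusion and exclusion criteria at the point of screening", and a screening log is kept. Section 7.0 states: "All infusion bags will be masked".

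The primary analysis in Section 26.0 is a simple t-test on the 24-week change in the sum of UPDRS subscales 1-3. A permutation test is mentioned as a possible addition. Section 5.0 lists the trial as closed.

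**The concern.** Alternation is deterministic, and the only departure from it is at one person's discretion. Nothing in the plan makes assignment a matter of chance, and nothing hides the next assignment from the person who makes it. Yet Section 9.0 (an exclusion window), Section 11.0 (an attendance rule) and Section 29.0 (a withdrawal rule) use *randomized* or *randomization*. A reader relying on those sections would credit the trial with a protection it does not have.

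At stake is whether a UPDRS difference can be attributed to yFFP. Without random, concealed allocation, a difference could also reflect which patients were placed in which arm. The fuller analysis plan promised in Section 25.0 cannot supply random allocation afterwards.

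**Working it through.** The plan has no power calculation to reproduce. Section 27.0 bases the sample size on availability and gives no alpha, SD or effect. The stated total agrees with the arms: 10 + 10 = 20.

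**Is there any random element?** Section 7.0 gives a fixed order plus discretion. Section 20.0 gives a ratio and an allocator. Sections 12.0, 13.0 and 15.0 concern masking of the product, and Section 21.0 concerns unblinding. None describes a random sequence, envelopes, a central system, an independent allocator or a record of overrides.

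**Who can foresee the next assignment?** Under strict alternation, one known assignment reveals the rest until an override. Someone guessing each assignment is right 19.5 to 20 times out of 20. Under a random 10:10 list, always guessing the arm that is behind is right about 12.3 times (20,000 simulations). It is an inference, though a strong one, that the Trial Manager knows the arms: matching patients to yFFP stock by blood type requires knowing who receives yFFP, and Section 21.0 makes the same person the contact for urgent unblinding.

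**Can patients be lost after allocation?** Yes. Allocation falls on day 0 with baseline testing, and the eligibility call may come up to 4 days after that testing. In addition, Section 7.0 says of the time after day 0: "The first infusion will be scheduled at most two weeks later". Section 11.0 withdraws anyone not infused by day 5. Counted from day 0, a first infusion between day 6 and day 14 is allowed by one section and leads to withdrawal under the other.

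**What reference set would a permutation test have?** Strict alternation allows 1 sequence with a fixed start, or 2 with a random start. The second is the mirror of the first and gives the same absolute difference, so the smallest two-sided p-value is 1. Overrides add sequences, but with no known probabilities. A random 10:10 list would allow C(20,10) = 184,756 sequences, with a smallest two-sided p-value of 2/184,756 = 0.000011.

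**How much could steering matter?** This is an illustration; alpha, k and g are all assumed. There are 10 patients per arm, no drug effect, and a two-sided 5% t-test with 18 df (critical t 2.101). Let k be the number of pairs steered and g the difference in expected change within a pair, in units of the within-arm SD of change.

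- Exchanging k pairs between arms otherwise balanced in expectation: shift = 2kg/10.
- Directing k pairs that would otherwise have been placed at random: shift = kg/10.
- Noncentrality = shift × √(10/2) = shift × √5.

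| Assumed steering | Shift (SD) | Noncentrality | False-positive rate |
|---|---|---|---|
| 1 pair, g = 1, directed | 1×1/10 = 0.10 | 0.224 | 5.5% |
| 3 pairs, g = 0.5, directed | 3×0.5/10 = 0.15 | 0.335 | 6.2% |
| 1 pair, g = 1, exchanged | 2×1×1/10 = 0.20 | 0.447 | 7.1% |
| 3 pairs, g = 0.5, exchanged | 2×3×0.5/10 = 0.30 | 0.671 | 9.7% |

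**The case against.** The route to bias is narrower than the words *open to selection bias* may suggest. The override is tied to blood type, and the documents do not link blood type to prognosis. An investigator, not the Trial Manager, judges eligibility, and bags are masked to clinical staff and participants. Nobody is shown both to know the next arm and to decide who enters. The false-positive figures rest wholly on assumed inputs and start at a slight 5.5%. Section 7.0 discloses the alternation openly and does not call the design randomised; the stray terms elsewhere are incidental. If day 1 means the scheduled infusion day, the day-5 limit could fit within the two-week window. Finally, allocation in a closed trial cannot be changed.

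Much of this is fair as a limit on size, and the documents do not show that bias occurred. The core point remains. Masking protects assessment after allocation and does not conceal the next assignment from the allocator. The screening log covers reasons for non-participation where patients give them; it is not said to record the assigned arm or an override. The favourable reading of the day numbering is not what Section 7.0 defines, so the sections still need to be reconciled. Closure limits the remedy to reporting but does not change what the comparison can support.

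**Conclusion.** The concern holds and must be fixed. Followed as written, the plan yields a non-randomised comparison with unconcealed allocation. The t-test can still be computed, but only as a model-based comparison. A permutation test would rest on assumed exchangeability and not on the design.

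That conclusion comes from the text of Sections 7.0 and 20.0 and needs no numerical assumption. The size of any bias is unknown. In the assumed scenarios the inflation runs from slight to about double the nominal 5%, depending on how many patients are steered and how far their prognosis differs.

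**What to change.** **For the closed trial:**

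- Describe it as non-randomised and correct the wording in Sections 9.0, 11.0 and 29.0.
- Report the actual allocation order, and each override and post-allocation exclusion with its reason where one is on record. The Section 10.0 log may supply some reasons. The identification numbers (Section 20.0) and dispensing records (Section 14.0) may help to reconstruct order and arms, but not the reasons for overrides.
- Show baseline UPDRS and blood group by arm.
- In Section 26.0, make the 24-week sum of UPDRS subscales 1-3, adjusted for the baseline sum, a firm analysis reported beside the planned t-test. The section now offers it only as a possibility. Label it as added after closure if results were already known.
- Do not present any permutation p-value as design-based.

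The cost is reporting work and one model term. Residual df fall from 18 to 17 and the critical t rises from 2.101 to 2.110. Since 2.110/2.101 = 1.004, intervals are about 0.4% wider at the same residual SD. Adjustment deals with measured baseline severity only and does not remove unmeasured selection.

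**For any further enrolment or reuse of the protocol:**

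- Replace alternation and the override in Sections 7.0 and 20.0 with a concealed computer-generated 1:1 list, for example one random 10:10 list.
- Have it held by someone independent of enrolment and preferably of the analysis. The blood bank, which already blinds supplies under Section 15.0, is one candidate; the statistician is possible but risks unblinding the analysis.
- Draw an assignment only after eligibility and compatible yFFP stock are confirmed. If stock is lacking, the patient waits unassigned.
- Reconcile the day-0, eligibility-call and first-infusion timing in Sections 7.0, 10.0 and 11.0.

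The cost is a short amendment and possible waiting for scarce product. The timeline may lengthen: eight months is about 34.8 weeks, and 34.8 − 24 = 10.8 weeks remain for set-up, recruitment and analysis.

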8.0 SECONDARY OBJECTIVES

Secondary objectives: are to achieve a better understanding of this technology including the following:

- Factors predicting a beneficial response
- Effects on additional outcome parameters quality of life, and short-term risk profile

**INTRAVENOUS young FRESH FROZEN PLASMA (yFFP®) INVESTIGATIONAL TREATMENT FOR
PARKINSON'S DISEASE
PROTOCOL FOR CONTROLLED STUDY**

Secondary outcomes will be:

- Adverse events
- Patient laboratory parameters
- Patient Global Impression of change
- Work interference (Stanford Presenteeism Scale)

All other outcomes are exploratory.

9.0 SUBJECT POPULATION

Inclusion criteria

- A. Diagnosis of mild or moderate Parkinson's disease, no greater than 2.5 on the Hoehn and Yahr score.
- B. Disease duration of 1 to 5 years.
- C. Failure to respond (poor efficacy or unacceptable side effects) to drugs recommended for the treatment.
- D. Willingness to confirm the use of adequate birth control while on the trial will be required in premenopausal women without evidence for an inability to become pregnant.
- E. Willingness to not start any other treatment for Parkinson's disease during the parallel part of the trial.
- F. Age 45 years and above.

Exclusion criteria

Any individuals meeting any of the following will be excluded from the study:

- A. Other significant disease, which in the view of the study doctor may make assessment of the efficacy of yFFP difficult.
- B. Unstable medical conditions.
- C. Must weigh at least 45.5 kg. Cannot weigh more than 130 kg.
- D. A severe disease state diagnosis
- E. Litigation. Patients in litigation will be excluded only if conclusion of that litigation is imminent during the course of the study.
- F. If patient is pregnant or breastfeeding.
- G. Complete IgA deficiency.
- H. Rare contraindications to yFFP therapy as per summary of product characteristics.
- I. Receiving yFFP for other reasons.
- J. Ongoing drug or alcohol abuse.
- K. Psychiatric disorder that could, in the judgement of the site investigator, interfere with successful study participation.

**INTRAVENOUS young FRESH FROZEN PLASMA (yFFP®) INVESTIGATIONAL TREATMENT FOR
PARKINSON'S DISEASE
PROTOCOL FOR CONTROLLED STUDY**

- L. Unwillingness or inability to complete the study or an inability to understand the questionnaires being used.
- M. Cancer other than basal cell carcinoma within the last 5 years. However, those patients who have received definitive treatment, such as curative surgery more than 6 months ago, with no known recurrence can be included.
- N. A history of hypercoagulable or thrombophilic clotting abnormalities.
- O. A history of thromboembolic events: ischemic stroke, confirmed myocardial infarction, pulmonary embolism; deep venous thrombosis except where immobility related (for example, after injury or operation).
- P. Unstable angina pectoris.
- Q. Medications that might react with yFFP such as blood thinners
- R. Renal failure or serum creatinine greater than 1.5 times the upper limit of normal at screening.
- S. Any medical condition that, in the opinion of the investigator, would make it unsafe for the patient to participate or which would interfere with assessment of the outcome measures.
- T. Participation in another interventional trial within 3 months of randomization. Participation in non-interventional studies is not a reason for exclusion.

10.0 SCREENING, RECRUITMENT AND CONSENT

Patients will be identified through the clinical site.

Strategies will be implemented to maximize awareness of the trial in the patient population and increase referrals to the recruiting centers (informative materials will be included as part of the study documents).

Patients will be given the "Patient Information Sheet" to read at least 24-hours before the screening visit, where they will be given the "Informed consent."

At the screening visit, there will be an opportunity for the participants to ask questions of a member of staff trained in all trial procedures, as delegated by the PI. The Principal Presenter or a co-investigator at each site will ensure that the participants meet the inclusion and exclusion criteria at the point of screening.

Patients will be telephoned within 2 days, and maximally 4 days after baseline testing to confirm eligibility to participate.

Screen failures may be rescreened ONLY where there is a short-term reason for ineligibility, such as non-availability for study visits due to planned holidays or an ongoing acute illness.

**INTRAVENOUS young FRESH FROZEN PLASMA (yFFP®) INVESTIGATIONAL TREATMENT FOR
PARKINSON'S DISEASE
PROTOCOL FOR CONTROLLED STUDY**

A screening log will be kept at site to document details of patients invited to be screened for participation in the study. For patients who decline or are ineligible, this will document any reasons available for nonparticipation (where provided). The log will ensure potential participants are only approached once.

The original signed consent form will be retained in the investigator site file, with a copy in the participant's medical notes, and a copy provided to the participant. The participant will specifically consent to their GP being informed of their participation in the study.

The right to refuse to participate without giving reasons will be respected.

11.0 STUDY MEDICATION

Placebo

Matching placebo infusions will be supplied by the Spectrum Plasma Blood Bank for the infusion. These will be identical in appearance to the active infusions - they will be indistinguishable by color and labeling of the infusion.

yFFP infusion

The experimental intervention is 12.5 ml/kg intravenous Spectrum Plasma yFFP, per each of two infusions (25 ml/kg total), in combination with ongoing normal standard treatment.

For reported side effects of Spectrum Plasma yFFP infusion, please refer to AABB Circular of Information.

Contraindications include:

Absolute contraindications to the use of yFFP are documented intolerance to plasma or its components or selective deficiency of immunoglobulin A (IgA).

Relative contraindications are Heart failure or pulmonary edema.

Additional Cautions

Patients should avoid citrus and highly acidic fruits (example: strawberries, blueberries, loganberries, cranberries, currants, gooseberries, pineapple etc.) before and for a day after their last infusion, as patient may experience a reaction due to citrate.

Selection and timing of dose for each participant

Solutions will be available in 200 ml Spectrum Plasma yFFP infusion bags or matching placebo bags. Both bags will be masked prior to infusion.

In exceptional circumstances, where a randomized patient does not attend for the first infusion on day 1, delay of the first infusion up to day 5 is acceptable.

**INTRAVENOUS young FRESH FROZEN PLASMA (yFFP®) INVESTIGATIONAL TREATMENT FOR
PARKINSON'S DISEASE
PROTOCOL FOR CONTROLLED STUDY**

Data collection timelines remain the same, regardless of when infusions are received. Any patient who has not received his/her trial infusion by day 5, that is, before day 6, will be withdrawn and not given trial medication.

All patients who receive $\geq 80\%$ of the target dose will be included in the per-protocol analysis.

yFFP or placebo will be infused intravenously at an initial rate of not more than 2 ml/minute for 15 minutes. If well tolerated, the rate of administration may be increased to 10-15 ml/minute for the remainder of the infusion.

Infusion rate adjustments can be made if patients experience mild adverse clinical effects, reducing to 2 ml /minute in the first instance and further if required, while aiming for sufficient time to complete the entire infusion in a single day.

The dosing is based on the patient weight, clinicians should refer to this table before administering the study drug

Weight range Min (in kg)	Weight Range Max (in kg)	Volume to be Administered (in ml)	Bags (200 ml) to be dispensed	Bags – Infusion 1	Bags - Infusion 2
45.5	55.4	1,400	7	4	3
55.5	65.4	1,600	8	4	4
65.5	75.4	1,800	9	5	4
75.5	85.4	2,200	11	6	5
85.5	95.4	2,400	12	6	6
95.5	105.4	2,600	13	7	6
105.5	115.4	2,800	14	7	7
115.5	125.4	3,200	16	8	8
125.5	135.4	3,400	17	8	9

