12.0 PACKAGING AND LABELING OF INVESTIGATIONAL MEDICINAL PRODUCT

Medicinal product will be supplied by Spectrum Plasma in Fresenius Kabi individual 200 ml bags, containing--yFFP and 23-27 ml dextrose solution of citric acid, or 0.1% Riboflavin in normal saline as a control solution. Each bag will be blinded during administration by the study site.

Packaging and labeling will be completed in accordance with FDA regulations and Current Good Manufacturing Practice (CGMP). Spectrum Plasma is a FDA-AABB & CLIA registered, audited and accredited blood bank that will supply the investigation with FDA approved [21CFR640.30] plasma exclusively collected from

**INTRAVENOUS young FRESH FROZEN PLASMA (yFFP®) INVESTIGATIONAL TREATMENT FOR
PARKINSON'S DISEASE
PROTOCOL FOR CONTROLLED STUDY**

healthy, 18-25 year old sex-identified volunteer donors in full compliance to AABB and State of Texas regulations. yFFP is a registered trademark of Spectrum Plasma, Inc.

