14.0 PRESCRIPTION OF THE MEDICINAL PRODUCT

Medication will be prescribed by an authorized study physician according to the protocol, using a trial-specific prescription. The volume to be dispensed per patient will be calculated according to patient weight (dosing-schedule Table) and the site investigator will dispense the required number of bags.

Participants will be informed of potential adverse reactions and advised to seek medical help and contact the research team, if required.

Patients will carry cards with an emergency 24-hour emergency phone number.

Documentation of prescribing and dispensing study medication shall be maintained for study records in the patient file and a copy of all documents will be sent to the Trial Manager.

A specific prescription must be submitted to the Spectrum Plasma Blood Bank no later than the day prior to the patient's infusion.

**INTRAVENOUS young FRESH FROZEN PLASMA (yFFP®) INVESTIGATIONAL TREATMENT FOR
PARKINSON'S DISEASE
PROTOCOL FOR CONTROLLED STUDY**

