16.0 ADMINISTRATION OF THE MEDICINAL PRODUCT

If site prefers to run a slower infusion than described above, this will not be considered a protocol violation.

Patients may be offered diphenhydramine orally prior to starting the infusion.

Patients must be under continuous nurse observation during the infusion; in cases where no reduction of the infusion rate is required, the average infusion duration for a participant of 75 kg to 90 kg body weight is about 1.5 to 2 hours.

In the event that patients do not receive their entire first infusion, either due to having to stop early because of time constraints arising from long infusion duration with a low rate, or because side effects are intolerable even with the lowest infusion rate, they should still be offered the second infusion. Details of the amount infused should be recorded in the notes section of the infusion form.

Where the infusion cannot be tolerated, and the patient wishes to not receive additional infusion, the patient is withdrawn from further infusion, but follow-up data will be collected until the end of the study.

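### The stated dose of 12.5 ml/kg in each of two infusions (25 ml/kg total) is not what the 200 ml bag table delivers, and the gap is mainly per infusion

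*Combined protocol and SAP*

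**What the plan says.** Section 7 sets out to evaluate yFFP at "12.5 ml/kg in each of two doses, two days apart (25 ml/kg total" and gives placebo at an equal volume. Section 11 repeats the dose as the definition of the experimental intervention: "12.5 ml/kg intravenous Spectrum Plasma yFFP, per each of two infusions (25 ml/kg total". Neither section qualifies the figure as approximate or gives a tolerance.

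Section 11 then supplies a table of nine weight bands, each with a volume, a bag count and a split of the bags between the two infusions. It says that "clinicians should refer to this table before administering the study drug". Section 14 makes the same table the basis for dispensing: "volume to be dispensed per patient will be calculated according to patient weight (dosing-schedule Table". No section explains how the table was derived from the per-kg figure or which of the two governs.

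Two further statements bear on the same reference. Section 12 describes the active bag as containing "yFFP and 23-27 ml dextrose solution of citric acid", without saying whether that solution is part of the 200 ml. Section 11 also says that patients who receive at least 80% "of the target dose will be included in the per-protocol analysis", without tying the target to the table volume or to 25 ml/kg times weight.

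**The concern.** The per-kg figure describes the intervention under test, and a reader of the results would take it as the dose given. The table is what staff use. If the two differ, a report that repeats the stated figure misdescribes what patients received.

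The statement has two parts, a total and an amount for each infusion, and each has to be checked against the table. Whole bags and weight bands will always produce some spread in the total. A separate question is whether the bags are divided so that each infusion can be 12.5 ml/kg.

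**Working it through.** **Inputs.** Stated dose: 12.5 ml/kg per infusion, two infusions, 25 ml/kg in total (Sections 7 and 11). Bag size 200 ml, bag counts and splits: Section 11 table. Eligible weights 45.5 to 130 kg: Section 9, exclusion C. The 200 ml is taken as the infused volume.

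**Internal consistency.** 2 x 12.5 = 25, so the stated figures agree with each other. In all nine rows, bags x 200 equals the tabulated volume and the two infusions add up to the bag count. The table has no addition error.

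**How the table relates to 25 ml/kg.** Bags needed at the band midpoint = 25 x midpoint / 200. For the first band this is 25 x 50.45 / 200 = 6.31, against 7 in the table. For the fourth it is 25 x 80.45 / 200 = 10.06, against 11. Rounding up reproduces all nine rows.

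**ml/kg by band.** Total = bags x 200 / weight; each infusion = its bags x 200 / weight. Ranges run from the top to the bottom of the band, with the last band cut at 130 kg.

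| Weight (kg) | Bags (split) | Total | Infusion 1 | Infusion 2 |
|---|---|---|---|---|
| 45.5-55.4 | 7 (4/3) | 25.27-30.77 | 14.44-17.58 | 10.83-13.19 |
| 55.5-65.4 | 8 (4/4) | 24.46-28.83 | 12.23-14.41 | 12.23-14.41 |
| 65.5-75.4 | 9 (5/4) | 23.87-27.48 | 13.26-15.27 | 10.61-12.21 |
| 75.5-85.4 | 11 (6/5) | 25.76-29.14 | 14.05-15.89 | 11.71-13.25 |
| 85.5-95.4 | 12 (6/6) | 25.16-28.07 | 12.58-14.04 | 12.58-14.04 |
| 95.5-105.4 | 13 (7/6) | 24.67-27.23 | 13.28-14.66 | 11.39-12.57 |
| 105.5-115.4 | 14 (7/7) | 24.26-26.54 | 12.13-13.27 | 12.13-13.27 |
| 115.5-125.4 | 16 (8/8) | 25.52-27.71 | 12.76-13.85 | 12.76-13.85 |
| 125.5-130 | 17 (8/9) | 26.15-27.09 | 12.31-12.75 | 13.85-14.34 |

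**Extremes.** Total: 1,800/75.4 = 23.87 ml/kg (95.5% of 25) and 1,400/45.5 = 30.77 ml/kg (123.1%). Single infusion: 800/75.4 = 10.61 ml/kg (84.9% of 12.5) and 800/45.5 = 17.58 ml/kg (140.7%).

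**Even grid, 45.5 to 130.0 kg in 0.1 kg steps, 846 weights.**
- Total above 25 ml/kg: 746 (88.2%).
- Total within 10% of 25: 692 (81.8%). Within 20%: 834 (98.6%). The other 12 weights are 45.5-46.6 kg.
- At least one infusion more than 10% off 12.5: 464 (54.8%). More than 20% off: 136 (16.1%).
- The same totals halved evenly, more than 10% off 12.5: 154 (18.2%).

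**Unequal splits.** In the five odd-count bands the two infusions differ by one bag, that is by 200/weight: 4.40 ml/kg at 45.5 kg and 1.54 ml/kg at 130 kg. Both therefore cannot equal 12.5 at any weight in those bands. The drop from 54.8% to 18.2% shows that the split, more than the total, produces the per-infusion gap.

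**The case against.** The strongest reply is that the table is itself the rounding rule. It gives every eligible weight one volume and one split, and it follows 25 ml/kg at the band midpoint throughout. A per-kg dose delivered in whole bags by 10 kg bands must vary within a band. This stands: staff have an instruction, and for the total the departure is modest. The 30.8 and 17.6 ml/kg extremes occur only at 45.5 kg, the eligibility floor. The 10% and 20% limits are the reviewer's yardsticks, since the documents give none. Even halves would need half bags in five bands, and each odd row already uses the closest whole-bag split, so the 18% shows where the gap comes from and is not a proposed scheme. None of this makes 12.5 ml/kg true of both infusions in those five bands, and the derivation of the table is not written down.

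Four stronger readings are tempting and are not supported:

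- **The comparison is biased.** Section 7 sets the placebo volume equal to the yFFP volume, so the mismatch alone does not favour an arm.
- **Patients received more than intended.** The documents do not say whether the per-kg figure or the table governs, and the grid does not describe the enrolled patients.
- **Plasma delivered fell below the stated dose.** If the 23-27 ml of citrate-dextrose lies inside the 200 ml and the per-kg figure means plasma alone, the total would run from 9 x 173 / 75.4 = 20.6 to 7 x 177 / 45.5 = 27.2 ml/kg. Neither assumption is stated. The table treats 200 ml per bag as the volume administered, and the placebo is matched on volume. This supports a clarification only.
- **The 80% rule misclassifies patients.** A full course is 100% of the table volume and at least 1,800 / (25 x 75.4) = 95.5% of 25 ml/kg times weight. Only incomplete courses could be affected: at 45.5 kg the threshold is 0.8 x 1,400 = 1,120 ml or 0.8 x 25 x 45.5 = 910 ml, depending on the reference. Section 26 names no per-protocol analysis.

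**Conclusion.** The point holds as a misstatement of the dose tested. In total, the table stays close to 25 ml/kg and is mostly above it. Per infusion, the stated 12.5 ml/kg cannot be met for both infusions in five of nine bands, and at least one infusion is more than 10% off at just over half of the grid weights.

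These sizes assume 200 ml infused per bag, complete infusions and weights spread evenly over 45.5-130 kg. The shares for the patients actually enrolled could be higher or lower, but the unequal splits do not depend on the weight distribution. No effect on the primary UPDRS comparison is shown. The correction is worth making because the figure defines the intervention and is easily put right.

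**What to change.** Reconcile the per-kg statement in Sections 7 and 11 with the table, both in total and per infusion, without presuming which is right. No dose is proposed here. Report the ml/kg dispensed per infusion and by arm, and the ml/kg infused where volumes were recorded.

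Two minor clarifications belong in the same edit: whether the 200 ml includes the citrate-dextrose solution, and what reference the target dose in the 80% rule uses.

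The cost is a text correction, two clarifications and one summary table. Section 14 already provides for the dispensing data: "Documentation of prescribing and dispensing study medication shall be maintained for study records in the patient file". For a first infusion that was not completed, Section 16 asks that "Details of the amount infused should be recorded in the notes section of the infusion form". Section 5 lists the trial as closed in January 2019, so the correction may have to go into the report. The downsides are that the stated dose may become nominal or a range, and that an incomplete infusion with no recorded volume cannot be converted to ml/kg.
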